7.4 Test Article(s) (Study Drug(s) and/or Study Device(s))

7.4.1 Description

The group receiving the ropivacaine 0.5% will receive 1 syringe containing 20mLs of ropivacaine 0.5%, and the group receiving the ropivacaine/epinephrine will receive 1 syringe containing 19.9mLs of ropivacaine 0.5% and 0.1 mLs of Epinephrine 1mg/mL for a total volume of 20mLs. The medications will be injected between muscle planes in the back using real time ultra sound guidance. Both medications have been approved by the FDA for many years, for this specific use, as well as for injection around nerve fibers. These medications have been used in billions of people in the world already, with a very robust safety record. In our institution, we use these medications routinely every day for a number of procedures, including ESP blocks.

7.4.2 Treatment Regimen

There will be no adjustment to dose. Every participant will receive the same amount of medications as prepared by the investigational Pharmacy. The medications will be injected using real time ultra sound guidance between two muscle planes in the back of the body, using a 22gauge needle.

7.4.3 Method for Assigning Subject to Treatment Groups

The subjects enrolled will be randomized into two groups by a computer-generated randomization list using SAS software (SAS Institute, Cary, NC):

Randomization groups

1. Group RE will have 20mL of **0.5% Ropivacaine with epinephrine** injected at the left or right T5 transverse process.
2. Group R will have 20mL of **0.5% Ropivacaine without epinephrine** injected at the left or right T5 transverse process.

7.4.4 Subject Compliance Monitoring

The study will be done in the CRC of the Penn State College of Medicine. (and the MRI suit of the Department of Radiology, where the MRI will be done. Completed May 2023) Once the participant is included in to the study, an intravenous access and continuous monitoring of vital signs (ECG, non-invasive blood pressure every 5 minutes, and pulse oximetry) will be established. Continuous monitoring and recording of vital signs will take place as follows: blood pressure and heart rate will be measured every 5 minutes, starting prior to performing the block, till 60 minutes after the block is performed, and every 15 minutes thereafter for the duration of the study.

7.4.5 Blinding of the Test Article

The randomization will be performed, using a sealed envelope technique, by the investigational pharmacy while preparing the medications. All subjects, the anesthesiologist performing the procedure, the radiologist, and the research coordinator collecting the data will be blinded and will not be aware of the details of the injection and allocation of the participants. In the event that the patient has a concerning reaction or becomes unstable in any fashion, the patient will be immediately unblinded and removed from the study.

7.4.6 Receiving, Storage, Dispensing and Return

7.4.6.1 Receipt of Test Article

The study drug will be prepared and dispensed in standard sterile way by the Investigational Pharmacy of the Milton S. Hershey medical center. The medications will be collected, by the study coordinator, in a container with the participant's number, and will be brought to the CRC on the day of the study prior to the administration of medications for the study.

7.4.6.2 Storage

Investigational Pharmacy personnel, study coordinator and investigator will only have access to the medications and there will not be any storage of the medications.

7.4.6.3 Preparation and Dispensing

The randomization will be performed, using a sealed envelope technique, by the investigational pharmacy while preparing the medications.

7.4.6.4 Return or Destruction of the Test Article

NA

7.4.6.5 Prior and Concomitant Therapy

None

8.0 Subject Numbers and Statistical Plan

8.1 Number of Subjects

12 subjects are needed to follow the study protocol through to completion. Up to 35 subjects may be enrolled to allow for loss of participants who complete the enrollment step, but do not proceed to receive the ESP block procedure.

8.2 Sample size determination

This is a pilot study and will use descriptive results of this study to plan for a larger randomized clinical trial in the future.

8.3 Statistical methods

Statistics: The statistical analysis will be performed using STATA 14.1 statistical software (StataCorp LP, College Station, TX) and Wilcoxon matched-pairs U test will be utilized for different MRI measurements and calculations. The χ^2 test will be used to analyze the differences between dermatomal anesthesia on hemi-thorax and abdomen.

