19.0 Adverse Event Reporting

20.0 Study Monitoring, Auditing and Inspecting

21.0 Future Undetermined Research: Data and Specimen Banking

22.0 References

1.0 Objectives

1.1 Study Objectives

The **primary objectives** of this study are to define the extent of dermatomal anesthesia and anatomical spread of injectate (as defined by MRI imaging) that is provided by an ESP block at the T5 level, using twenty milliliters of 0.5% ropivacaine. MRI data will not be collected after May 2023

The **secondary objectives** include: 1) the measurement of changes in hemodynamic parameters associated with the ESP block, 2) the duration of sensory effects provided by ropivacaine with or without epinephrine, 3) the venous plasma concentration of ropivacaine at various time intervals after completion of the ESP block.

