1.2 Primary Study Endpoints

Outcomes to be assessed

1. Extent of dermatomal sensory loss
2. Duration of sensory loss
3. Anatomical extent of injectate spread using MRI imaging. MRI data will not be collected after May 2023
4. Venous plasma concentration of ropivacaine at periodic time intervals

We are comparing these outcomes between

1. 20ml ropivacaine 0.5% with epinephrine vs no epinephrine

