Study subjects will report to the Clinical Research Center (CRC) of Milton S. Hershey hospital on the day of their scheduled study procedure. Once they are checked in to CRC and ascertained that they followed fasting instructions, the female participants will be asked to take pregnancy test using a urine sample and a standardized pregnancy testing kit. Once the pregnancy test is determined to be negative, they will be considered to be a study participant. If pregnancy test is positive, they will be excluded from the study. Once the participant is included in to the study, an intravenous access and continuous monitoring of vital signs (ECG, non-invasive blood pressure every 5 minutes, and pulse oximetry) will be established. 3 ml of blood will be obtained from the Intravenous line already placed in the subject prior to performing the block. These samples will be repeated at 20, 40, 60, 90, 120, and 240 minutes after completion of the injection of active drug. A member of the research team will manually transport the appropriately-

labeled blood collection tube to a storage freezer in the Perioperative Genomics Laboratory (C2813, C2848) during the transport, blood samples will be placed in Category A sealed triple packaging. During transport, the specimen tubes will be placed in splash-proof and leak-proof containers. These primary containers are placed inside of secondary containers which will be sealed. The blood samples will be processed and analyzed for ropivacaine level using HPLC at genomic laboratory of department of Anesthesia, Hershey medical center at a later date. The results of the level of the ropivacaine level will be used for analysis of the results for the study. The subjects will not receive the results of these tests. However, if any of the subjects if specifically request for the results of these test that will be given to them. The blood samples will be immediately destroyed after the results of the ropivacaine conc. in the samples is obtained. The additional blood from samples, if any, will be destroyed.

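### Section 8.3 gives no between-arm summary or test for plasma concentration or sensory duration, no method for hemodynamics, and a chi-squared test that does not name the arms

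*Combined protocol and SAP*

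**What the plan says.** Section 1.2 lists four primary outcomes (extent of sensory loss, its duration, MRI spread, venous plasma ropivacaine) and then states "We are comparing these outcomes between" one contrast: "20ml ropivacaine 0.5% with epinephrine vs no epinephrine". Section 1.1 separately gives duration with or without epinephrine as a secondary objective. Section 7.1.1 randomizes six subjects to each of two parallel groups, RE and R, stratified so that left and right blocks are equal in each arm.

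Section 8.3 is the entire analysis plan and has two methods:

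- A "Wilcoxon matched-pairs U test will be utilized for different MRI measurements and calculations". On MRI, section 1.1 says "MRI data will not be collected after May 2023".
- A chi-squared test "to analyze the differences between dermatomal anesthesia on hemi-thorax and abdomen".

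Data collection continues for the other outcomes. For plasma, a pre-block sample is taken and section 7.2.1 adds: "These samples will be repeated at 20, 40, 60, 90, 120, and 240 minutes after completion of the injection of active drug". Sensation is checked at 20, 60, 120, 240 and 360 minutes. For vital signs, section 7.4.4 has "blood pressure and heart rate will be measured every 5 minutes, starting prior to performing the block", and every 15 minutes after the first hour. Hemodynamics is a secondary endpoint in section 1.3, and its objective in 1.1 concerns changes associated with the block.

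Section 8.2 calls the study a pilot whose descriptive results will be used to plan a larger trial. It does not say which summaries, or that they are given by arm.

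**The concern.** The study randomizes, blinds and stratifies in order to compare two arms, yet the analysis section never mentions those arms. Followed as written, it yields a matched-pairs analysis of an outcome no longer collected and a test about body regions. Plasma concentration and duration bear most directly on what epinephrine does, and neither is assigned a summary measure, an estimate or a test.

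At stake is how the results can be read. With no definition of the plasma summary, of duration or of the hemodynamic summary, each choice would be made after the data are seen, in a sample of 12 where such choices can change the impression. A pilot meant to inform a larger trial needs between-arm estimates and their precision, and 8.3 does not say it will produce them.

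**Working it through.** **1. Declared comparison against stated method.**

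| Outcome | In the 1.2 arm comparison? | Still collected? | Method in 8.3 |
|---|---|---|---|
| Extent of sensory loss | Yes | Yes | Chi-squared, worded by region; arms not named |
| Duration | Yes | Yes | None |
| MRI spread | Yes | No, stopped May 2023 | Wilcoxon matched-pairs |
| Plasma ropivacaine | Yes | Yes | None |
| Hemodynamics (1.3) | No | Yes | None |

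Three of the four declared outcomes are still collected. Two of these three have no method.

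**2. No figure to reproduce beyond the sample size.** 6 + 6 = 12 agrees with section 8.1. The plan gives no alpha, power, effect size or SD. Everything below assumes a two-sided 5% level and is illustrative.

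**3. Matched pairs in a 6 v 6 parallel design.** No subject in RE is paired with one in R. If six arbitrary pairs were formed, the smallest two-sided signed-rank p-value is 2/2^6 = 0.031. For the independent-groups rank-sum test it is 2/C(12,6) = 2/924 = 0.0022. Simulated power with normal data (20,000 runs) at a true difference of 1 SD is 0.20 for the arbitrary pairs and 0.30 for the exact rank-sum test.

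**4. Chi-squared test read by arm.** With 6 per arm and c subjects positive in total, the expected counts are c/2 and (12 - c)/2. The smaller is largest at c = 6, where it equals 3. Enumerating all 6 v 6 tables at a common response rate p, actual size is the sum of Bin(a; 6, p) x Bin(b; 6, p) over the rejecting tables:

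| p | Uncorrected chi-squared | Fisher |
|---|---|---|
| 0.3 | 0.068 | 0.003 |
| 0.4 | 0.063 | 0.005 |
| 0.5 | 0.058 | 0.006 |

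Neither is attractive. A count of blocked dermatomes per subject, compared by rank, keeps more information.

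**5. What 6 v 6 can support.** Exact rank-sum power is 0.20, 0.30, 0.58 and 0.83 at differences of 0.8, 1.0, 1.5 and 2.0 SD. The t test reaches 80% power only at 1.80 SD. Estimation is the realistic aim.

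**6. Stratifying by side.** Equal sides mean 3 left and 3 right per arm. Within each side, 3 of 6 subjects are RE, so there are C(6,3)^2 = 20^2 = 400 allocations. The smallest two-sided permutation p-value is 2/400 = 0.005, so a stratified exact comparison is workable.

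**7. Baseline covariate for a vital-sign summary.** The post-block schedule in 10.4 has 12 five-minute readings (5 to 60) and (360 - 60)/15 = 20 later ones, 32 in all, plus a pre-block value. In units of the within-arm SD of the summary, the 95% CI half-width for the arm difference is:

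- unadjusted: t(0.975, 10) x sqrt(2/6) = 2.228 x 0.577 = 1.29
- adjusted: t(0.975, 9) x sqrt[(2/6)(1 - r^2)(1 + 1/8)], with t = 2.262 and r the correlation with the pre-block value

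| Assumed r | Half-width (SD) |
|---|---|
| 0.3 | 1.32 |
| 0.5 | 1.20 |
| 0.7 | 0.99 |
| 0.8 | 0.83 |

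Break-even: 1 - r^2 = (2.228/2.262)^2 / 1.125 = 0.862, so r is about 0.37. Below that, adjustment widens the interval. The documents give no value of r.

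**The case against.** The strongest reply is section 8.2. This is a descriptive pilot with no stated hypothesis, so a missing test is not in itself a fault. That stands. What it does not excuse is that no by-arm description is defined either, while 8.3 does name tests.

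A second reply is that 8.3 may mean more than it says. The chi-squared sentence could intend arm differences assessed in each region, which would fit 1.2. The Wilcoxon name mixes a paired test with the U of the independent-groups test. A paired test could also suit each subject's 30- and 90-minute scans among MRI data already obtained. These readings are possible, so a reader should not take it as certain that no test was ever meant to compare the arms. Even on the generous reading, plasma concentration and duration remain uncovered.

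Three stronger inferences are tempting and are not supported:

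- **That the plan leaves an epinephrine question on hemodynamics unanswered.** Hemodynamics is outside the 1.2 list and its objective refers to the block. It is an endpoint with no method, not a failed declared comparison.
- **That false positives will multiply across time points.** Periodic intervals describe when measurements are taken. The plan proposes no test at each time and states no alpha, so an inflated error rate is not a consequence of the plan.
- **That pre-block values are wasted.** The pre-block plasma sample precedes any study ropivacaine and should be near zero, so it offers nothing to adjust for. For vital signs, the objective of measuring changes already implies a reference value, and a covariate helps only above a correlation of about 0.37.

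The entry under 10.7 that statistical tests are not applicable belongs to safety monitoring and does not settle the matter.

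**Conclusion.** The point holds in a limited form. Section 8.3 does not say how the comparison declared in 1.2 will be made for two of the three outcomes still collected, is ambiguous for the third, and is silent on hemodynamics. That follows from the text and needs no assumption. The poor fit of the named tests to two independent groups of six follows from the design: no between-arm pairing, and a smaller expected count of at most 3.

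The power, test-size and CI figures rest on an assumed two-sided 5% level. The power and CI figures also assume normal data, the test-size figures a common response rate of 0.3 to 0.5, and the adjusted half-widths an assumed baseline correlation. They show what the design can support and do not show that 12 subjects is wrong, since no power inputs are given. The text should be corrected before any unblinded analysis. The defect is recoverable because the data are being collected.

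**What to change.** Reword 8.3 to give one RE-versus-R estimate with a 95% CI per outcome, one value per subject, in keeping with the pilot aim:

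- **Plasma:** log of the observed maximum and log AUC over 0-240 minutes, reported as geometric mean ratios.
- **Extent:** number of blocked dermatomes, with the assessment used stated in advance (for example the largest count over the five). Compare by exact Wilcoxon-Mann-Whitney or permutation, stratified by side.
- **Duration:** last assessment with reduced sensation, with subjects still blocked at 360 minutes sharing the top tied rank. Use the same stratified exact comparison. Only five assessment times exist, so ties will be heavy. The probability that an RE subject outlasts an R subject, ties counted as half, is a safer estimate than a difference in minutes.
- **Hemodynamics:** a prespecified summary of the post-block readings for each vital sign, described as change from the pre-block value, and by arm with that value as covariate.
- **MRI:** say how scans obtained before May 2023 will be reported, or remove the test.

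Show individual time points descriptively.

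The cost is a rewrite of one section, with no new data, visits or subjects. The covariate takes one degree of freedom and loses a little precision if the baseline correlation is below about 0.37. Adding side to that model takes another: at r = 0.5 the half-width is t(0.975, 8) x sqrt[(2/6)(0.75)(1 + 1/7)] = 1.23 SD instead of 1.20.

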7.0 Study Design and Procedures

7.1 Study Design

This will be a randomized, blinded, controlled study.

This study will examine the effects of **single injections** of 0.5% ropivacaine with epinephrine or without epinephrine (20 ml of each) injected at ESP at the T5 vertebra level.

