7.1.1 Randomization process

The subjects enrolled will be randomized into two groups (6 participants in each group) by a computer-generated randomization list using SAS software (SAS Institute, Cary, NC):

Randomization groups

1. Group RE will have 20mL of **0.5% Ropivacaine with epinephrine** injected at the left or right T5 transverse process.
2. Group R will have 20mL of **0.5% Ropivacaine without epinephrine** injected at the left or right T5 transverse process.

The randomization will be performed, using a sealed envelope technique, and will be stratified according to the side of the injections (either left or right) so that each arm will have equal number of left and right sided ESP blocks. This will be done by the investigational pharmacy while preparing the medications. All subjects, the anesthesiologist performing the procedure, the radiologist, and the research coordinator collecting the data will be blinded and will not be aware of the details of the injection and allocation of the participants. In the event that the patient has a concerning reaction or becomes unstable in any fashion, the patient will be immediately unblinded and removed from the study.

The conduct of the study will be as follows.

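### Section 8.3 names no between-arm analysis for the extent of sensory loss; its only test for that endpoint is an unpaired chi-square of hemi-thorax against abdomen in the same subjects.

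*Combined protocol and SAP*

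**What the plan says.** Section 1.2 puts "Extent of dermatomal sensory loss" first among four primary endpoints, without ranking them, and gives the comparison for these outcomes as "20ml ropivacaine 0.5% with epinephrine vs no epinephrine". Section 7.1 describes a randomized, blinded, controlled study: "This study will examine the effects of single injections of 0.5% ropivacaine with epinephrine or without epinephrine". Section 7.1.1 adds "The subjects enrolled will be randomized into two groups (6 participants in each group") and says that randomization is "stratified according to the side of the injections (either left or right"), with equal numbers of left and right blocks in each arm. Section 8.1 states that "12 subjects are needed to follow the study protocol through to completion".

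Section 7.2.1 scores cold sensation as reduced or normal at 20, 60, 120, 240 and 360 minutes.

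Section 8.3 is the whole statistical methods text and names two tests. For imaging, a "Wilcoxon matched-pairs U test will be utilized for different MRI measurements and calculations". For sensory extent, the chi-square "test will be used to analyze the differences between dermatomal anesthesia on hemi-thorax and abdomen". Neither sentence mentions the arms, a unit of analysis or a time point. Section 10.7, which says that statistical tests do not apply, belongs to the safety monitoring plan and adds nothing here. Section 8.2 calls the study a pilot whose descriptive results will be used to plan a larger randomized trial.

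**The concern.** The comparison declared in Section 1.2 and the contrast tested in Section 8.3 are different. One sets arm against arm. The other, as worded, sets one body region against another. Each subject has one injection, so both regions are scored in the same person after the same block, and a Pearson chi-square assumes they are independent.

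At stake is whether the pilot delivers what its successor needs: an arm difference in sensory extent and its spread between subjects. Section 8.3 specifies neither. With MRI collection stopped in May 2023 (Sections 1.1 and 1.2), this chi-square is also the only named test for any outcome still being collected.

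**Working it through.** The plan gives no alpha, power, effect size, block rate or variance, so it has no figure to reproduce. What can be checked is how the named test behaves under each reading of the sentence.

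**Inputs from the plan:** 12 subjects, 6 per arm; one injection each; equal left and right blocks within each arm, hence 3 + 3; binary scores at five times.
**Assumed:** two-sided 0.05; block rates, correlations, dermatomes per subject and SDs as stated below.

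**Reading 1, the literal one: thorax against abdomen, all 12 subjects.**
- Let each region be blocked with probability p, with within-subject correlation r. The difference in the number of subjects blocked has variance 2 × 12 × p(1 − p)(1 − r). The chi-square uses 2 × 12 × p(1 − p). For positive r it overstates the variance by a factor 1/(1 − r), which is 2 at r = 0.5.
- Enumerating all outcomes of 12 pairs gives the type I error (uncorrected chi-square):

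| r | p = 0.5 | p = 0.7 |
|---|---|---|
| 0 | 6.4% | 4.9% |
| 0.3 | 2.7% | 2.0% |
| 0.5 | 1.0% | 0.7% |
| 0.7 | 0.15% | 0.1% |

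The size is wrong, and for positive correlation the test is too conservative. No arm term enters.

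**Reading 2: arm against arm within each region, one binary result per subject.**
- If m of 12 subjects are blocked, the expected counts in each arm are m/2 and (12 − m)/2. The smaller is largest at m = 6, where it is 3. The usual minimum of 5 fails for every possible outcome.
- Enumerating the 7 × 7 tables gives a maximum size of 6.8% for the uncorrected chi-square, at a common rate near 0.3 or 0.7. For Fisher's exact test the maximum is 0.6%.
- Examples: 3/6 against 6/6 gives chi-square p = 0.046 and Fisher p = 0.18; 1/6 against 5/6 gives 0.021 and 0.080.

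**Reading 3: dermatomes pooled as units in an arm comparison.**
- Assume 12 dermatomes per subject with a mean of 6 blocked, so 6 × 12 = 72 units per arm. Pooling treats each subject's count as binomial, with SD √(12 × 0.5 × 0.5) = 1.73. The true SD between subjects decides the direction of the error.
- Simulated trials (counts drawn from a normal distribution, rounded and limited to 0–12; pooled two-proportion test) give:

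| Between-subject SD | Type I error |
|---|---|
| 1 | 0.1% |
| 1.5 | 3% |
| 1.73 | 6% |
| 2 | 10% |
| 2.5 | 18% |
| 3 | 25% |

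**Feasibility of a per-subject analysis.** With 3 + 3 per side there are 20 × 20 = 400 equally likely allocations, so the smallest two-sided p from a side-stratified exact test is 2/400 = 0.005. Ignoring side it is 2/924 = 0.002.

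**The case against.** The strongest defence is purpose. Section 8.2 promises descriptive results from a pilot, and no alpha, power or decision rests on this p-value. Section 1.1 states the primary objective as defining the extent of anesthesia; among the objectives, epinephrine appears only under the secondary one on duration. Descriptive summaries of two randomized arms could show the comparison in Section 1.2 without a test. This stands, and it limits the severity. It does not supply the missing between-arm method, and the plan does choose to name a test.

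Second, the sentence may be loose wording for comparing the arms within each region. That is possible and cannot be excluded. It is a reason to rewrite the sentence, because on that reading the expected counts are still too small and the unit and time point are still undefined.

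A reader might infer that the named test inflates false positives, perhaps to 25%. The documents do not support this. That figure needs an SD of 3 and pooled dermatomes, and the plan gives no SD and does not say that dermatomes will be pooled. The literal test is conservative when the regions are positively correlated, and even pooling falls below 5% for SDs under about 1.7. The 6.8% for a single 6 versus 6 table is a modest excess. A reader might also infer that the trial can give no answer on epinephrine and sensory extent. That too goes beyond the text: what is missing is a named method, and the data for one will be collected.

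**Conclusion.** The concern holds in this form: Section 1.2 declares an arm comparison of sensory extent, and Section 8.3 names no method for it. The test it does name uses the wrong contrast and, read literally, treats paired observations as independent. Its error rate is not the nominal one, but the direction depends on what is counted: mostly conservative for region against region, up to 6.8% for a single arm table, and either way for pooled dermatomes. All sizes rest on an assumed two-sided 0.05. The first also rests on assumed block rates and correlations, and the last on an assumed 12 dermatomes, a mean of 6 and SDs from 1 to 3. The missing arm contrast rests on no assumption beyond reading the sentence as written. Severity: should fix, given the descriptive pilot aim.

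**What to change.** Replace the chi-square sentence in Section 8.3 with:

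> For each subject, count the dermatomes with reduced cold sensation at one pre-specified assessment (or the maximum over the five assessments). Report the R versus RE difference (Hodges-Lehmann or median difference) with an exact or permutation 95% confidence interval. If a p-value is given, use an exact rank-sum or permutation test that respects the stratification by side. Any thorax versus abdomen contrast is within subject and uses a paired method, such as the exact McNemar test. Dermatomes and time points are not treated as independent units.

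The sponsor must choose between a named assessment and the maximum before looking at the data by arm; otherwise five tests remain possible. If the McNemar test is kept, the plan must also define when a region counts as blocked.

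No subjects or procedures are added. The costs are a coarser p-value (smallest two-sided value 0.005 with 3 + 3 per side) and a little more code, chiefly for a side-stratified interval with tied integer counts.
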